Malignant tumors are often associated with weakness and cachexia. The clinical characteristic changes of tumor cachexia are continuously skeletal muscle reduction, which can not be corrected by routine dietary supplement, which may cause progressive functional decline and disorder [3]. Sarcopenia is defined as skeletal muscle mass (SMM) combined with skeletal muscle dysfunction. Now it is considered that the occurrence of primary sarcopenia is mainly related to age, and the occurrence of secondary sarcopenia is related to systemic acute and chronic diseases. In recent years, according to the latest definition of the Asian Working Group for Sarcopenia, the definition of sarcopenia has been clarified, the ICD code of the disease has been defined, and a unified diagnosis has formed [4]. Clinical studies on sarcopenia and cancer have also attracted more attention, such as digestive tract tumor, pancreatic cancer, gastric cancer, urologic tumors and rectal cancer [5][6]. Data had show that the prevalence of sarcopenia in lung cancer patients can reach as high as 43%, although sarcopenia is an elderly syndrome closely related to age, clinical rehabilitation or dietitian intervention diet can improve the nutritional status of patients with lung cancer to a certain extent. Although the diagnostic criteria of sarcopenia have been confirmed, most of the research are limited to the toxic and side effects of chemotherapy, postoperative complications and the survival rate of sarcopenia and other malignant tumors. There are few studies that have attempted to

investigate the impact of sarcopenia on the prognosis of lung cancer. Previous studies have also found that nutritional status plays an important role in tumor cachexia of other systems [7]. Loss of appetite, weight loss and fatigue caused by tumor will lead to poor nutritional status or even malnutrition. Poor nutritional status will further reduce patients' appetite and physical activity, thus forming a vicious circle. Nutrition is also an important factor in the progression of sarcopenia disease. Therefore, it is also of great clinical significance to determine whether nutritional status will affect the prognosis of patients with tumor sarcopenia, so it is absolutely valuable to investigate the risk factors associated with sarcopenia in lung cancer patients and confirm the impact of nutritional status on prognosis among these patients.

It has been reported that the prevalence of malnutrition in cancer patients varies from 30% to 80% according to the different distribution characteristics of the enrolled population in different studies [8]. A systematic review from 2006 to 2017 found that the Physical function and nutritional status were the most predictive domains for mortality [9]. At the same time, MNA score is widely used in tumor research of all ages [10], and it has been proved that MNA nutritional assessment can simply and quickly evaluate the nutritional status of patients according to anthropometric values, basic activity ability and eating conditions, and form a relatively complete evaluation system combined with blood albumin and other values [11], The score is also used to evaluate the baseline nutritional status of a variety of tumors and has good prognostic value in clinical outcome [12]. In rectal cancer, head and neck cancer and even non solid tumors such as acute lymphoblastic leukemia, higher MNA score has been proved to be an independent risk factor of prognosis [13]. Regarding the close relationship between this evaluation method and multiple clinical complications and prognostic factors, in recent years, people have gradually realized that early screening of the nutritional status of tumor patients and further receiving an appropriate intervention are particularly important to improve the influences on the outcomes of tumors. The American Society of Clinical Oncology also recommended the routine application of MNA score in the basic evaluation of nutritional status of 65 year old patients receiving chemotherapy in 2020 [7]. However, the application of this scoring system in early and mid-term lung cancer is very limited, studies examining the clinical features and nutritional status of patients in early mid-term NSCLC are thus necessary.

Therefore, this study aims to observe the correlation between sarcopenia and the

prognosis of patients with early mid-term non-small cell lung cancer, clarify the value of sarcopenia and nutritional status in predicting the overall survival rate and progression-free survival rate of patients with non-small cell lung cancer, and explore the value of early screening and nutritional intervention in predicting the prognosis of patients with lung cancer, To provide evidence-based research for alleviating the social and economic burden of lung cancer patients.

2、Research purpose

1. Identify the prevalence of sarcopenia in patients with early and mid-term non-small cell lung cancer as well as the anthropometry, clinical characteristics, tumor stage and treatment methods of this population, to compare and analyze the differences of clinical characteristics such as smoking status, tumor stage, EGFR gene expression, nutritional score and physical endurance with patients with non-small cell lung cancer.
2. Multivariate logistic analysis aim to explore the related risk factors of sarcopenia in patients with early and mid-term non-small cell lung cancer.
3. To clarify the impact of sarcopenia on the overall survival rate and progression-free survival rate of early and mid-term non-small cell lung cancer, and its clinical value as a predictor of the prognosis of patients.

3、Type of experimental design, grouping method

- 1) Study case collection scope: including respiratory ward, respiratory intensive care unit and respiratory outpatient department of Huadong Hospital Affiliated to Fudan University.
- 2) This study was a prospective, and observational cohort study. The follow-up results were grouped according to the diagnostic criteria of sarcopenia.

4、Case inclusion criteria and exclusion criteria

1. inclusion criteria

- (1) The patients with non-small cell lung cancer diagnosed by cytology or pathology meet the standards of clinical diagnosis and treatment guidelines for lung cancer of Chinese Medical Association (2018 Edition), and the TNM staging diagnosis of lung cancer meets the stage IA-IIIA.

(2) The medical records are complete.

2. exclusion criteria

- (1) Severe heart failure, acute progressive pulmonary inflammation ,acute liver and kidney dysfunction in recent 2 weeks;
- (2) Incomplete clinical and follow-up data or disagreement or inability to conduct regular follow -up CT imaging evaluation;
- (3) Patients with other malignant tumors and a history of related tumor chemotherapy within half year, previous history of radiotherapy;
- (4) Unable to stand or walk, unable to cooperate to complete the walking test, and patients with past unconscious fall history and fall risk;
- (5) Unable to complete BIA examination due to pacemaker implantation and other reasons;
- (6) Those who withdraw from the study for subjective reasons, regardless of the patient's loss of follow-up caused by any reason, shall be regarded as patients who withdraw from the study.

5、 Estimation of case sample size

Prevalence of lung cancer in China is about 36.09/10 million, with mortality of 28.41/10 million. The prevalence of sarcopenia in Asia is 25.2%. Combined with reported correlation coefficient OR3.2 of tumor and sarcopenia, GPOWER is used to calculate the incomplete information and missing value below 10%. α Less than or equal to 0.05 and statistical inspection force $1 - \beta$ When it is 0.8, it is estimated that the final required numbers for this study includes about 66 patients with lung cancer complicated with sarcopenia. According to the 1:1 ratio of sarcopenia and non sarcopenia, the overall sample size is about 132, so as to ensure that the efficiency of the control test is 80%.

6、 Research process

1. Demographic data

The gender, age, height, weight, body mass index and skeletal muscle mass index were recorded.

2. Clinical data

According to the Electronic Medical Record, system image record data, face-to-face or

telephone follow-up records, clinical data were collected: oral drugs, smoking status (no smoking history, past smoking history, now smoking), tumor stage at the time of diagnosis, other chronic diseases, tumor pathological type and stage. According to the definition of tumor, lymph node and metastasis TNM stage in the eighth edition of American Lung Cancer joint staging. ECOG (Eastern Cooperative Oncology Group performance status, PS), MNA (mini nutritional assessment) nutrition score, quality of life depression score and treatment strategy.

3. Examination data

Serological samples: blood routine, C-reactive protein, blood cholesterol level, albumin level, tumor markers CEA, cyfra211, NSE, SCC, EGFR gene expression.

Imaging examination: chest CT.

4. Diagnostic criteria of sarcopenia

The diagnosis process of sarcopenia complies with the provisions of the Asian sarcopenia working group. The specific information collected for diagnosis includes: skeletal muscle mass of limbs: the skeletal muscle mass index (ASMI) is measured by Korea inbody570 (Korea Biospace) human composition analyzer. The decrease of skeletal muscle mass is defined as the decrease of male $< 7.0\text{kg}/\text{m}^2$ and female $< 5.7\text{kg}/\text{m}^2$; The Jamar hand dynamometer (USA) is used to measure the grip strength in the grip strength test. Patients are required to hold the grip strength tester in the dominant hand with standing position for 3 times, the maximum value were recorded. Male $< 28\text{kg}$ and female $< 18\text{kg}$ are defined as reduced grip strength; The time required for patients to walk at normal pace was measured by 6-meter distance pace measurement; If the walking speed is less than $0.8\text{m}/\text{s}$, it is defined as the decline of walking function; The decrease of ASMI accompanied by the decrease of grip strength or gait speed was diagnosed as sarcopenia.

5. Follow up endpoint

The primary endpoint was progression free survival (PFS) within 2 years, defined as the time from diagnosis to clinically recorded disease progression or death from any cause. The patients were followed up according to the outpatient and electronic medical records and telephone calls. The tumor treatment strategy and the time of clinical outcome or disease progression were followed up. The disease progression was defined as the 20% increase in sum of longest diameters from nadir (and a minimum absolute increase of 5 mm), or unequivocal increase in nontarget lesions according to RECIST solid tumor standard. The progress needs to be confirmed by at least one imaging and one clinical expert. The deadline for follow-up is 2 years. The secondary endpoint was overall survival time (OS), defined as

the outcome of patient death from diagnosis to any cause or the final follow-up time. During the follow-up, the researchers conducted disease evaluation, follow up of disease progress, grip strength test, walking test, muscle density measurement and nutritional score (MNA) at 6, 12, 18 and 24 months after enrollment. If feasible, the participants will continue to be followed up for up to five years.

7、Adverse events

1. During the walking test, trained doctors and nurses were trained to detect the exercise safety in the whole process. This study will practically implement the safety work and safety equipment in the implementation of the scheme, including oxygen inhalation, oximeter, defibrillator, cardiopulmonary resuscitation drugs, bronchodilators and nitroglycerin; In case of the following conditions, the test will be terminated strictly: 1. Reaching 85% of the maximum heart rate; 2. Arrhythmia events; 3. Blood pressure exceeding 180 / 100mmhg; 4. Chest pain; 5. Blurred vision; 6. Cold sweat syncope; 7. Abnormal limb coordination; 8. Blood oxygen saturation lower than 85%.
2. This study is an observational study and does not involve new drugs and traumatic testing, so there is basically no additional research risk. In case of acute exacerbation or condition change during the study, the patient may not be affected by the study and be treated in accordance with the medical principles. The end point of observation and disease progress indicators are the objective state of the development of the disease itself. The study does not involve any research methods and drugs for intervention and diagnosis measures, so there will be no serious adverse events related to the study.

8、Statistical analysis

The patients were divided into two groups according to whether they were diagnosed as sarcopenia, and the differences of clinical data between the two groups were analyzed. The statistical analysis will be calculated by spss24.0 statistical analysis software.

1. Demographic characteristics and clinical data analysis: describe the age and gender distribution of patients, group patients according to whether they are diagnosed as sarcopenia, and analyze the differences of clinical data such as age distribution, smoking, tumor type and clinical stage between the two groups. Continuous variables are represented by mean standard deviation, classified variables are represented by

percentage, students t-test analysis and Mann-Whitney U test are used according to data type differences, and chi square test is used for component comparison of classified data.

2. Analysis of risk factors of non-small cell lung cancer combined with sarcopenia: univariate and multivariate logistic analysis of relevant variables of patients with sarcopenia, including clinical data variables, nutritional status, tumor stage, serum C-reactive protein, cholesterol level, albumin level, EGFR gene expression, etc, Logistic regression was used to analyze the risk factors of sarcopenia in non-small cell lung cancer.
3. Prognostic value of sarcopenia in non-small cell lung cancer: progression free survival time PFS and overall survival time OS were statistically analyzed by Kaplan-Meier, and the difference was tested by log-rank method.

9、 Ethics related to experiment

The risk of patients participating in this study comes from the risk of tumor itself and tumor complications. It is an observational study without any intervention means such as drugs. The study itself does not increase the disease risk of patients. Patients can still stop treatment or withdraw from the study at any time, and subjects can stop the study at any time or for any reason at their own request or at the request of the investigator. For all subjects who withdrew from the study for any reason, contact themselves or their families or health care providers 24 weeks after withdrawal to determine the subject's life status. Subjects may voluntarily stop participating in the study at any time without affecting further treatment.

At the same time, ensure that after the end of the study and midway suspension, all participants continue to accept the disease medical measures recommended in the guidelines, do not change the follow-up further treatment, and do not intervene in the outcome of the disease.

10、 Recruitment methods and informed consent of subjects

This study used the recruitment method of clinical case collection, including respiratory ward, respiratory intensive care unit and respiratory clinic. All patients must

obtain informed consent and sign the informed consent form.

11、Expected progress and completion time of the study

Study period: October 15, 2021 to October 15, 2024

From October 2021 to November 2021, the research group collected personnel training and enrolled cases.

From November 2021 to November 2023, the case observation indexes, clinical data and follow-up data were collected.

From November 2023 to January 2024, the final follow-up was completed and the outcome events were collected and sorted out.

From January 2024 to October 2024, statistics and data sorting, writing papers, accepting results and publishing articles.

12、Follow up and medical measures after the study

After the study, continue to accept the disease medical measures recommended by the guidelines, do not change the follow-up further treatment, and do not intervene in the outcome of the disease.

13、Responsibilities of each party and other relevant provisions

1. Research Division of labor: before the beginning of the research, the researchers shall be trained to be familiar with the research scheme and the principles of data collection. The researcher shall record the contents truthfully, in detail and carefully as required. The specific division of labor is as follows:

- [name], attending physician, research plan formulation, data collection and article writing
- [name], deputy chief physician, supervision and training of research program
- [name], resident patient follow-up and data management
- [name], attending physician, data collection, statistics and article writing

2. Expected goals

1) The purpose of this study is to clarify the impact of skeletal sarcopenia on the overall survival rate and progression free survival rate of early and mid-term non-small cell lung

cancer, as well as its clinical value in predicting the prognosis of patients.

- 2) The research results will provide high-quality evidence-based medicine evidence for the formulation, revision and optimization of international and domestic lung cancer clinical guidelines and expert consensus, and the research has certain social value.
- 3) While further cultivating the clinical trial research team, the research team will publish at least 2 clinical research papers as the first / corresponding author in the International Journal of respiratory medicine consistent with the funding direction of the project.
- 4) At least one provincial and municipal project in the direction of relevant disciplines of the new project.
- 5) Make special or general assembly speeches at important international conferences in this field.

14、References

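### Exclusion (2), read literally, drops enrolled patients from the 2-year PFS analysis because their follow-up is incomplete, and no PFS analysis set or censoring date is stated that would settle the matter

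*Combined protocol and SAP*

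**What the plan says.** Section 3 describes a prospective observational cohort, grouped by sarcopenia status.

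- **Section 4, exclusion (2):** "Incomplete clinical and follow-up data" is a reason for exclusion. Unwillingness or inability to have regular follow-up CT comes after it as a separate alternative.
- **Section 4, inclusion (2):** "The medical records are complete".
- **Section 4, exclusion (6):** "loss of follow-up caused by any reason, shall be regarded as patients who withdraw from the study".
- **Section 5:** the sample size allows for "incomplete information and missing value below 10" per cent.
- **Section 6, item 5, primary endpoint:** "progression free survival (PFS) within 2 years, defined as the time from diagnosis to clinically recorded disease progression or death from any cause". The follow-up deadline is 2 years.
- **Section 6, item 5, OS:** "the outcome of patient death from diagnosis to any cause or the final follow-up time".
- **Section 6, item 5, conduct:** "The patients were followed up according to the outpatient and electronic medical records and telephone calls", with assessments "at 6, 12, 18 and 24 months after enrollment".
- **Section 8, item 3:** PFS and OS are analysed by Kaplan-Meier and compared by the log-rank test.
- **Section 9:** everyone who withdraws is to be traced for life status 24 weeks later.

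**The concern.** In a prospective cohort, nobody knows at entry whether a patient's 2-year follow-up will be complete. A criterion that excludes for incomplete follow-up can therefore be applied in full only after the event, by removing people already enrolled. Item (6) makes this reading realistic, because withdrawal and loss also happen only after enrolment and yet stand in the exclusion list.

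If lost patients are removed, their event-free time goes with them and event rates look slightly too high. The comparison by sarcopenia status shifts if loss differs between the groups. That is plausible for an exposure defined partly by weak grip or slow gait, although the documents give no figure. If loss is related to prognosis, the shift can go either way.

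What is at stake is the primary analysis population. It depends on which section is followed, and as the text stands that choice could be made after outcomes are known.

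**Working it through.** **1. The passages side by side**

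| Text | Points to |
|---|---|
| Exclusion (2), follow-up data | Removal, if literal; no effect on later losses, if an entry check |
| Inclusion (2), complete records | Same doubt, since follow-up itself runs through the medical records |
| Exclusion (6) | Loss is labelled withdrawal; deletion of data is not mentioned |
| OS definition, final follow-up time | Keeping and censoring, for OS |
| Kaplan-Meier, 2-year deadline | Censoring, but only of patients left in the dataset |
| 24-week contact | Further information on withdrawn patients is wanted |
| PFS definition | Silent on censoring |

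An entry check is conceivable because PFS starts at diagnosis while visits are counted from enrolment, so some follow-up could already exist at entry. The documents do not say which is meant. Nor do they say who is in the PFS analysis, when a patient lost before 2 years is censored, or whether a death found at the 24-week contact is a PFS event.

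**2. The plan's own figure**

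With 25.2% and OR 3.2 (section 5), the second proportion is 0.252 × 3.2 / (1 − 0.252 + 0.252 × 3.2) = 0.519. A two-sided 5% test (two-sided is my assumption) with continuity correction and 80% power needs 59 per group. Then 59 / 0.90 = 65.6, so 66 per group and 132 in total, as stated. The plan thus expects incomplete cases, but the allowance does not say how they are analysed.

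**3. Size of the effect of deletion**

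Assumed, not in the documents: exponential event and loss times, 25% events in 2 years in both groups (true HR 1.00), loss L of 5% (non-sarcopenic) and 15% (sarcopenic), unrelated to prognosis.

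- Event hazard λ = −ln(0.75)/2 = 0.1438 per year.
- Loss hazard μ = −ln(1 − L)/2 = 0.0256 and 0.0813.
- Proportion removed = μ/(λ+μ) × [1 − 0.75(1 − L)] = 4.4% and 13.1%. The average is 8.7%, about 11 of 132, which is within the plan's allowance.
- Proportion with an observed event = λ/(λ+μ) × [1 − 0.75(1 − L)] = 0.2440 and 0.2316.
- Event proportion among those kept = 0.2440/0.9565 = 0.2551 and 0.2316/0.8691 = 0.2665, against a true 0.25.
- Ratio of cumulative hazards = ln(1 − 0.2665)/ln(1 − 0.2551) = 1.05.

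The Cox hazard ratio under the same assumptions is 1.055 by numerical integration. Simulation agrees and gives 1.00 when the same patients are censored at loss.

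**4. Sensitivity of that figure**

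- Equal 10% loss: 1.00 with deletion; the event proportion rises to about 26% in both groups.
- 15% or 40% events with 5% and 15% loss: about 1.06 and 1.05.
- Loss pattern reversed: 1/1.055 = 0.95.
- Larger loss, 10% and 30%: 1.13 with 20% events and 1.11 with 40%. This removes about 16% to 18% of patients, beyond the plan's 10%.
- Removal related to prognosis, with 4.35% and 13.05% removed: if none of those removed would have had an event, ln(1 − 0.25/0.8695)/ln(1 − 0.25/0.9565) = 1.12. If half would have, ln(1 − 0.18475/0.8695)/ln(1 − 0.22825/0.9565) = 0.88.

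**5. Against sampling error**

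Expected events are 0.25 × 132 = 33, so the SE of log HR is about 2/√33 = 0.348. Then ln(1.055)/0.348 = 0.15 SE, and the two prognosis-related cases are 0.3 to 0.4 SE.

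**The case against.** The strongest reply is that exclusion (2) is an entry check. Its second half concerns willingness and ability to have follow-up CT, which is judged at screening, and several other passages make sense only if lost patients stay in. This stands as a possible reading, so a reader should not infer that the plan intends to delete lost patients or that its primary result will be biased. It does not remove the conflict: the first half of the item is separate from the CT clause, and item (6) shows that the list holds post-enrolment rules.

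A reader might also infer that the plan ignores losses altogether. It does not: item (6) classes them as withdrawals and section 9 traces life status. Only their handling in the PFS analysis is missing.

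Third, it can be said that Kaplan-Meier already implies censoring. It does, but only for patients not removed beforehand.

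Last, the effect is small and rests on assumed rates. Exclusion (4) already removes patients who cannot stand or walk, and follow-up can use records and telephone, so differential loss may be limited. This is fair, and it is why the point rests on the unsettled analysis population and not on a demonstrated bias.

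**Conclusion.** The point holds as a conflict in the text plus an omission, and it should be fixed. Followed literally, exclusion (2), with item (6) beside it, selects the 2-year PFS population on post-baseline information. Other sections point the other way, and no PFS analysis set or censoring date decides between them. Confidence in this is high; the documents do not show which reading was intended.

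The likely effect is modest: a hazard ratio of about 1.06 in place of 1.00 under 25% events and 5% against 15% loss unrelated to prognosis, about 0.15 of a standard error, and essentially none if loss is equal. All these rates are assumptions.

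It would go too far to say that one treatment of deaths learned of after loss is the only correct one. Suppose event-free patients are censored at their last six-monthly visit, with 20% or 50% of the event hazard being direct death and the same loss rates. Counting every later death within 2 years then gives 1.02 to 1.04 in simulation, and not counting them gives 1.01 to 1.02. Both are below deletion, and neither is exactly 1.00.

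**What to change.** 1. Delete the follow-up-data words from exclusion (2).
2. State that the remaining completeness criteria (incomplete clinical data, complete medical records in inclusion (2), and the follow-up CT clause) are judged only on information available at enrolment.
3. Move item (6) to a withdrawal section which says that data up to withdrawal or loss are kept.
4. Define the analysis set as every enrolled eligible patient with a baseline sarcopenia assessment.
5. For PFS, censor patients without an event at the last evaluable disease assessment or at 2 years from diagnosis, whichever is earlier. For OS, censor at the last date known alive.
6. Decide before analysis whether deaths learned of after loss are PFS events, and run the other choice as a sensitivity analysis.
7. Report loss and its timing by sarcopenia group.

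The cost is protocol and SAP wording; the life-status contact is already planned. Some short follow-up times will enter the analysis, and censoring assumes non-informative loss. That assumption matters little in the cases tried: if half the patients have three times the event hazard and loss is three times more, or three times less, frequent among them, censoring at loss gives 0.99 or 1.02, against 1.04 or 1.08 with deletion. These changes do not address time between diagnosis and enrolment, which still counts as time at risk.

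### The 66 per group and the 80% power rest on a tumour–sarcopenia comparison that the study does not make, so the 80% does not apply to the log-rank test of PFS

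*Combined protocol and SAP*

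**What the plan says.** Section 5 (Estimation of case sample size) has two substantive inputs: "The prevalence of sarcopenia in Asia is 25.2" per cent, and an odds ratio, "Combined with reported correlation coefficient OR3.2 of tumor and sarcopenia, GPOWER is used". It adds a significance level of 0.05, power of 0.8 and an allowance described as "incomplete information and missing value below 10" per cent. The result is that "it is estimated that the final required numbers for this study includes about 66 patients with lung cancer complicated with sarcopenia". A 1:1 ratio of sarcopenia to no sarcopenia then gives 132, "so as to ensure that the efficiency of the control test is 80" per cent.

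The rest of the plan describes a different comparison:

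- Section 4 admits only patients with stage IA–IIIA non-small cell lung cancer.
- Sections 3 and 8 group them by whether they meet the sarcopenia criteria.
- Section 6, item 5 states: "The primary endpoint was progression free survival (PFS) within 2 years".
- Section 8, item 3 analyses PFS and overall survival by Kaplan-Meier and log-rank.

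**The concern.** An odds ratio between tumour and sarcopenia treats tumour as the exposure and sarcopenia as the outcome. Every participant here has a tumour, so the study cannot estimate that odds ratio. The comparison it does make has sarcopenia as the exposure and time to progression or death as the outcome. The power of that comparison depends on the hazard ratio, the number of events and the split between the groups. Section 5 supplies only the last of these, and does so by assumption.

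Section 5 is the plan's only justification of sample size and its only power statement. If the PFS comparison is not significant, a reader who trusts the 80% will take the result as evidence from an adequately powered study that sarcopenia has no prognostic effect. Section 13 says the results are meant to inform clinical guidelines, so that misreading would matter.

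**Working it through.** **1. Reproducing the 66.** Inputs from section 5: prevalence 0.252, odds ratio 3.2, alpha 0.05, power 0.80, 10% loss. Sidedness and the test are not stated.

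- Odds without tumour: 0.252/0.748 = 0.3369. Odds with tumour: 3.2 × 0.3369 = 1.078. Prevalence with tumour: 1.078/2.078 = 0.519.
- Two-sided pooled formula, n = [1.96√(2p̄(1−p̄)) + 0.8416√(p₁(1−p₁)+p₂(1−p₂))]²/(p₂−p₁)², with p₁ = 0.252, p₂ = 0.519, p̄ = 0.385: n = 51.05, so 52 per group.
- With continuity correction: 58.3, so 59.
- Two-sided Fisher exact: power 0.797 at n = 58 and 0.807 at n = 59, so 59.
- Allowing for 10% loss: 59/0.9 = 65.6, so **66**, the stated figure.

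Other variants, after dividing by 0.9, do not give 66: two-sided uncorrected 58, unpooled 55, arcsine 57; one-sided uncorrected 46, continuity-corrected 54, Fisher 52.

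**2. What the 66 counts.** In this calculation the groups are people with and without a tumour, and sarcopenia is the outcome. Section 5 attaches the same number to lung cancer patients with and without sarcopenia.

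**3. What the log-rank test needs.** Schoenfeld's formula, two-sided 0.05, 80% power, share π with sarcopenia: events d = (1.96 + 0.8416)²/[π(1−π)(ln HR)²]. At π = 0.5 this is 31.40/(ln HR)².

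| HR | (ln HR)² | Events needed at 1:1 |
|---|---|---|
| 1.5 | 0.1644 | 191 |
| 2.0 | 0.4805 | 65.3, so 66 |
| 2.5 | 0.8396 | 37.4, so 38 |

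The 66 events for HR 2.0 happen to equal the 66 patients per group. The two numbers are unrelated.

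**4. Power at the planned size.** The documents give no event rate, so I assume that a proportion p₀ of 15–40% of non-sarcopenic patients have a PFS event within 2 years. I also assume proportional hazards and 132 × 0.9 ≈ 119 evaluable patients at 1:1. The sarcopenic event proportion is 1 − (1 − p₀)^HR, and power is Φ(√(d/4) × ln HR − 1.96).

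Example, p₀ = 0.15 and HR 2.0: the sarcopenic proportion is 1 − 0.85² = 0.2775; d = 59.5 × (0.15 + 0.2775) = 25.4; power = Φ(2.52 × 0.693 − 1.96) = Φ(−0.21) = 42%.

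| p₀ | Power, HR 1.5 | Power, HR 2.0 | Power, HR 2.5 | HR detectable with 80% power |
|---|---|---|---|---|
| 15% | 16% | 42% | 69% | 2.76 |
| 20% | 19% | 52% | 80% | 2.50 |
| 30% | 26% | 67% | 92% | 2.20 |
| 40% | 33% | 78% | 96% | 2.03 |

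With all 132 evaluable, power for HR 2.0 is 45–82% over the same range.

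**5. The 1:1 split.** Patients are grouped by diagnosis, and no quota or matching is described. At the 25.2% prevalence in section 5, HR 2.0 needs 87 events and power at N = 119 is 29–61%. At the 43% quoted in the introduction for lung cancer, it needs 67 events and power is 40–76%.

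**The case against.** **The derivation is inferred.** Section 5 names no test, sidedness or inflation rule, and it speaks of loss below 10%, not equal to 10%. The match needs a two-sided Fisher or continuity-corrected calculation and division by 0.9; multiplying 59 by 1.1 gives 64.9, so 65. This is fair. The exact match is strong evidence, not proof. The main point does not need it, because whichever routine was run, the stated inputs contain nothing about PFS.

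**The 80% is not expressly tied to PFS.** Section 5 names no endpoint, and section 2 lists prevalence and risk factors before survival. But an odds ratio for tumour does not fit those aims either: tumour status does not vary in this cohort, so it cannot be a coefficient in the logistic model. With PFS named as primary, readers will attach the only power statement to it.

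**PFS power may be adequate.** This stands. At HR 2.5 power is 69–96% over the assumed range, and at HR 2.0 it reaches 85% if half the non-sarcopenic patients have an event. The study has not been shown to be underpowered; its power for PFS is simply not established.

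**The harm is conditional and no procedure changes.** Also true. It is why the remedy is small, but it does not make the stated 80% correct.

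**Conclusion.** The concern holds. The sample-size inputs describe an association between tumour and sarcopenia that a cohort made up only of lung cancer patients cannot test, and the 80% does not carry over to the log-rank comparison of PFS. This mismatch follows from the documents alone.

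The size of the gap rests on assumptions, because no hazard ratio or event rate is given: two-sided 0.05, proportional hazards, 119 evaluable patients at 1:1 and 15–40% two-year events without sarcopenia. On those, 80% power is available only for hazard ratios of about 2.0 to 2.8. For HR 1.5 power is at most about one third. A split nearer 25% sarcopenia lowers power further. Higher event rates or a stronger effect would raise it.

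**What to change.** Rewrite section 5 for the planned analysis and keep N at 132:

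- Delete the statement that 132 patients give 80% power, or attach it explicitly to the tumour–sarcopenia hypothesis and say that this study does not test it.
- State the assumed 2-year PFS event proportion with its source, the expected share of patients with sarcopenia, and the number of events these imply.
- Give the smallest hazard ratio detectable with 80% power, or the power for a named hazard ratio, for the two-sided log-rank test by Schoenfeld's formula. Show it at 1:1 and at the expected sarcopenia share, since the event requirement for HR 2.0 moves from 66 to 87 between an even split and 25.2%.
- Take the assumptions from outside sources, not from this cohort's observed results.

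The cost is one rewritten paragraph, with no extra patients and no change to procedures. For moderate hazard ratios at the event rates assumed above, the stated power will be less favourable than 80%.
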